7.3.2.2 DINAMO Mono

Secondary endpoints of DINAMO™ Mono are defined in [Section 5.1.2](#).

The secondary endpoint of time to treatment failure will be analysed and graphically described by Kaplan-Meier estimates up to the planned end of the study. A descriptive Log-rank test will compare linagliptin 5 mg and pooled empagliflozin versus placebo individually up to Week 26. Patients in the placebo group will be censored after 26 weeks unless a prior treatment failure is observed. Data obtained after re-randomisation in the placebo group will not be utilised for the determination of time to treatment failure.

The change in HbA1c from baseline to the end of 26 weeks will be analysed based on a REML approach using MMRM to assess the effectiveness and efficacy, using the same sensitivity methods as described in [Section 7.3.4.1.1](#) and [Section 7.3.4.1.3](#) respectively.

[figure not shown]
It is expected that a large group of drug naïve patients will require early intervention of rescue medication as early as first on-treatment visit, therefore the change in HbA1c from baseline to the end of 26 weeks will also be analysed using an ANCOVA model including treatment as a fixed classification effect, baseline HbA1c as a linear covariate, and age as a categorical covariate. The missing data will be imputed by the last on-treatment observation without rescue medication carried forwards. In case, there is no on-treatment observation without rescue medication, baseline value will be carried forward.

The following secondary endpoints will be analysed using the same methods described in [section 7.3.2.1](#).

- Change in FPG (mg/dl) from baseline to the end of 26 weeks
- Change in body weight (kg) from baseline to the end of 26 weeks
- Change in SBP (mmHg) from baseline to the end of 26 weeks
- Change in DBP (mmHg) from baseline to the end of 26 weeks

The change in FPG (mg/dl) from baseline to the end of 26 weeks will also be analysed using an ANCOVA model including treatment as a fixed classification effect, baseline FPG as a linear covariate, and age as a categorical covariate. The third approach will have any post-baseline missing values, off-treatment values and values after rescue medication imputed by BOCF since FPG is measured only at baseline and Week 26.

The proportion of patients who achieve HbA1c < 7.0% and < 6.5% at the end of 26 weeks will be determined per treatment group and the risk difference of active treatments versus placebo will be determined and assessed by an exact 2-sided 90% confidence interval.

7.3.6 Safety analyses

Adverse events will be coded using the Medical Dictionary for Regulatory Activities (MedDRA) coding dictionary. Standard BI summary tables and listings will be produced. In general, safety analyses will be descriptive in nature and will be based on BI standards. No hypothesis testing is planned.

Statistical analyses and reporting of adverse events will concentrate on treatment-emergent adverse events. To this end, all adverse events occurring between start of treatment and end of the residual effect period will be considered 'treatment-emergent'. The residual effect period is defined as 7 days after the date of the last dose of trial medication. Adverse events that start before first drug intake and deteriorate under treatment will also be considered as 'treatment-emergent'. All AEs occurring before first study medication intake will be assigned to 'pre-treatment' and all AEs occurring after last study medication intake plus 7 days will be assigned to 'post-treatment'.

Frequency, severity, and causal relationship of adverse events will be tabulated by system organ class and preferred term after coding according to the current version of MedDRA.

Laboratory data will be analysed both quantitatively as well as qualitatively. The latter will be done via comparison of laboratory data to their reference ranges. Values outside the reference range as well as values defined as clinically relevant will be highlighted in the listings. Treatment groups will be compared descriptively with regard to distribution parameters as well as with regard to frequency and percentage of patients with abnormal values or clinically relevant abnormal values.

Vital signs, physical examinations, or other safety-relevant data observed at screening, baseline, during the course of the trial and at the end-of-trial evaluation will be assessed with regard to possible changes compared to findings before start of treatment.

The safety analyses will be performed using the following population set and randomised study treatment combinations according to the defined period, separately for DINAMO™ and DINAMO™ Mono.

- **Comparison vs. placebo:** All patients in the TS will be included in the safety analyses up to Week 26 presented by placebo, linagliptin 5 mg and empagliflozin pooled.
- **Safety during active treatment periods:** All patients on active treatment at anytime in the TS will be included in the safety analyses up to Week 52 presented by linagliptin pooled and empagliflozin pooled. For patients on active treatment and initially randomised to placebo at the start of the study, analyses will be restricted to data collected after Week 26.
- **Assessment of up-titration to empagliflozin 25 mg (For DINAMO™ only):** Patients initially randomised to empagliflozin in the TS, excluding the responders at Week 12 and the patients who did not proceed to re-randomisation at Week 14, will

be included in the safety analyses from Week 15 to Week 52 presented by empagliflozin 10 mg and 25 mg non-responder at Week 12 after initial randomisation.

- **Long term safety:** All patients in the TS, excluding patients initially randomised to placebo, will be included in the safety analyses up to Week 52 presented by linagliptin 5 mg and empagliflozin pooled.

7.3.7 Pharmacokinetic and pharmacodynamics analyses

In order to complement the pharmacokinetic characterisations of linagliptin and empagliflozin in paediatric patients with T2DM, in a first step, a descriptive analysis of the plasma concentrations will be performed to allow for a comparison to adults. In a second step, a population PK analysis may be conducted if the descriptive analysis suggests meaningful differences in the PK of adolescents compared to adults.

No pharmacodynamics analyses are planned.

PK analyses will be performed in the treated patients. Further information regarding the statistical analysis will be documented in the TSAP.

7.4 INTERIM ANALYSES

No interim analysis is planned, but the conduct of the trial will be monitored by a DMC.

7.5 HANDLING OF MISSING DATA

The handling of missing data in the primary and secondary analyses is described in [Section 7.3.1](#) and [Section 7.3.2](#) respectively.

Details regarding the imputation rule for further endpoints will be specified in the TSAP.

Missing or incomplete AE data will be imputed according to BI standards. Other missing safety data will not be imputed.

7.6 RANDOMISATION

At visit 2, patients will be randomised in blocks to double-blind treatment. Approximately equal numbers of patients will be randomised to each treatment group. The randomisation will be stratified by age (<15 years; ≥15 to <18 years). It will be monitored and capped so that at least 30% but no more than 70% of the randomised patients are < 15 years. For DINAMO™ only, the randomisation system will also include caps for gender so that at least 30% but no more than 70% of the randomised patients are girls.

At visit 4B, patients from the empagliflozin 10 mg arm who do not achieve an HbA1c < 7.0% at Week 12 will be re-randomised in blocks to double-blind treatment with either empagliflozin 10 mg or empagliflozin 25 mg. This re-randomisation will be stratified by age at baseline (< 15 years; ≥ 15 to <18 years). Practically, an IRT call will be performed for all patients to maintain double-blind conditions but only patients on empagliflozin 10 mg with HbA1c ≥ 7.0% at Week 12 may get new trial treatment re-assigned.

At visit 5, patients from the placebo arm will be re-randomised in blocks to double-blind treatment. Approximately equal numbers of patients will be re-randomised to empagliflozin 10 mg, empagliflozin 25 mg, or linagliptin 5 mg. The re-randomisation will be stratified by age at baseline (<15 years; ≥15 to <18 years). Practically, an IRT call will be performed for all patients to maintain double-blind conditions but only patients on placebo may get new trial treatment re-assigned.

BI will arrange for the randomisation and the packaging and labelling of trial medication. The randomisation list will be generated using a validated system, which involves a pseudo-random number generator so that the resulting treatment will be both reproducible and non-predictable. The block size will be documented in the Clinical Trial Report (CTR). Access to the codes will be controlled and documented. The method of assigning patients to treatment groups is described in [Section 4.1.3](#).

7.7 DETERMINATION OF SAMPLE SIZE

7.7.1 DINAMO

To support the sample size determination various sample size scenarios were considered. The underlying assumptions and the power estimates for the final sample size are described in details in this section for the “wash out” effectiveness analysis. These estimates are based on available study data in adults with T2DM treated with placebo, linagliptin or empagliflozin.

Sample size calculation for the “wash out” effectiveness analyses

Based on the “wash out” analysis, the superiority of pooled empagliflozin doses (empagliflozin 10 mg, empagliflozin 25 mg) and the superiority of linagliptin 5 mg compared to placebo will be tested simultaneously using the Hochberg procedure at the study-wise alpha level of 0.05 (see [section 7.2.1](#)).

For the corresponding power considerations post-rescue data will be included, and it will be assumed that there is no treatment difference for off-treatment patients. Average treatment effects including HbA1c values after the start of rescue therapy can be obtained from the studies quoted below and are summarised in Table [7.7.1: 1](#). The corrected treatment difference in this table was calculated assuming patients discontinuing active treatment show the same HbA1c change from baseline as the average placebo patient.

In Table 7.7.1: 1 HbA1c results are summarised as a basis for the efficacy analysis. Where available data for Week 24 are quoted, otherwise for Week 18:

- Study 1218.17, patients treated with linagliptin 5 mg or placebo in combination with metformin background therapy [[U09-2533-03](#)]
- Study 1218.36, patients treated with linagliptin 5 mg or placebo in combination with basal insulin therapy [[c02697848 ; U11-2286-01](#)]
- Study 1245.23, patients treated with empagliflozin 10 mg, empagliflozin 25 mg, or placebo in combination with metformin background therapy only [[U12-1518-01](#)]

- Study 1245.33, patients treated with empagliflozin 10 mg, empagliflozin 25 mg, or placebo in combination with basal insulin therapy [[U12-3817](#)]
- Study 1245.49, patients treated with empagliflozin 10 mg, empagliflozin 25 mg, or placebo in combination with insulin or metformin background therapy [[U13-2122](#)]

Studies 1218.17, 1218.36 and 1245.23 assessed the change from baseline to Week 24 as primary endpoint, in studies 1245.33 and 1245.49 the primary endpoint was change from baseline to Week 18. For all calculations raw means and standard deviations for the primary endpoint were considered as initial basis for further calculations.

Table 7.7.1: 1 HbA1c (%) change from baseline to Week 18 or 24 for studies with T2DM patients treated with linagliptin or empagliflozin

Study number	Placebo			Active treatment				Corrected treatment difference ⁴
	N	Mean ¹	SD ²	N	Mean ¹	SD ²	N disc. ³	Mean Active - Placebo
1218.17 - Week 24 linagliptin 5 mg	156	-0.07	1.03	471	-0.66	0.85	39	-0.54
1218.36 - Week 24 linagliptin 5 mg	560	0.01	0.93	568	-0.66	0.89	36	-0.63
1245.23 – Week 24 empagliflozin 10 mg	183	-0.26	0.79	206	-0.76	0.76	8	-0.48
1245.33 – Week 18 empagliflozin 10 mg	145	0.06	0.89	152	-0.69	0.88	16	-0.68
1245.49 – Week 18 empagliflozin 10 mg	173	-0.59	0.85	170	-1.04	0.79	17 ^a	-0.41

¹ Mean change from baseline in HbA1c at Week 18 or 24 based on the observed means in the raw data (including post rescue medication data)

² Observed standard deviation in the raw data up to Week 18 or 24 (including post rescue medication data)

³ Number of patients prematurely discontinuing active treatment prior to endpoint visit according to report disposition table

⁴ Assuming placebo response for patients prematurely discontinuing active treatment

^a Number of patients excluded from full analysis completers set, estimate of treatment discontinuations up to Week 18

Based on these results a mean treatment difference in HbA1c change from baseline of -0.55% with a SD of 0.9% between active drugs and placebo can be assumed. For the effectiveness analysis a covariate adjusted standard deviation of 0.9% can be regarded as the expected scenario, while 0.8% will probably be optimistic. A conservative scenario of 1.0% is added because of the potential of increased variability through the multiple imputations performed for the “wash out”. Power estimates in [Table 7.7.1: 2](#) are based on a two-sided t-test at alpha-level of 0.05. Additionally the power is given for the alpha-level of 0.025 to provide a lower bound of the expected power due to the Hochberg correction for multiplicity.

Table 7.7.1: 2 Power estimates for various scenarios for the “wash out” effectiveness analysis

Alpha (2-sided)	Treatment effect (%)	Covariate-adjusted standard deviation (%)	Sample size per group	Power
0.05	-0.55	1.00	50	77%
0.05	-0.55	0.90	50	85%
0.05	-0.55	0.80	50	92%
0.025	-0.55	1.00	50	68%
0.025	-0.55	0.90	50	78%
0.025	-0.55	0.80	50	87%

Summary

The final sample size of 50 randomised patients per group was chosen as a balance of clinical, regulatory, ethical, feasibility and statistical considerations. The objective is to minimise exposure of children, given that the available paediatric population is also limited in number, while maintaining acceptable statistical properties.

Calculations were performed using nQuery Advisor® 7.0 statistical package by [REDACTED]

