The primary endpoint of the final analysis was the change from baseline in HbA1c (%) after 12 weeks of treatment. Because of the early termination of the study, the trial had limited statistical power. After 12 weeks of treatment, the adjusted mean treatment difference between linagliptin 5 mg and placebo was -0.63 (95% CI: $-1.50, 0.23$; $p = 0.1447$). The adjusted mean treatment difference between linagliptin 1 mg and placebo was -0.48 (95% CI: $-1.47, 0.51$; $p = 0.3295$). As expected because of the limited power of the trial, a statistically significant difference to placebo could be demonstrated neither for the linagliptin 1 mg dose nor for the linagliptin 5 mg dose. The reduction of -0.63 with linagliptin 5 mg is considered clinically meaningful. The results were in accordance with data from adult patients after 12 weeks of treatment with linagliptin 5 mg. The median change from baseline in HbA1c (%) was $+0.50$ in the placebo group, -0.05 in the linagliptin 1 mg group, and -0.30 in the linagliptin 5 mg group. The difference to placebo was -0.80 in the linagliptin 5 mg group compared with -0.55 in the linagliptin 1 mg group. The results were consistent with data from adult patients after 12 weeks of treatment with linagliptin 5 mg. In the linagliptin 5 mg group, a reduction in HbA1c compared with baseline was seen over the entire randomised treatment period. In contrast, HbA1c had returned almost to baseline in the linagliptin 1 mg group and had increased beyond baseline HbA1c in the placebo group at Week 12. The percentage of patients with a relative efficacy response (HbA1c lowering by at least 0.5%) was greater in the linagliptin 5 mg group (30.8%) than in the linagliptin 1 mg group (20.0%) or placebo group (14.3%). Furthermore, the proportion of patients who had a baseline HbA1c $\geq 7\%$ and reached target HbA1c $< 7\%$ (absolute efficacy response) was greater with linagliptin 5 mg (36.4%) than with placebo (18.2%), whereas it was 10.0% with linagliptin 1 mg. A target HbA1c $< 7\%$ is more difficult to achieve for patients with a higher baseline HbA1c value than for patients with a lower baseline HbA1c value.

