7.2.1.2 Secondary family of hypotheses

After having obtained statistically significant results for both hypotheses $H_{0,1}$ and $H_{0,2}$ of the primary family of hypotheses, the following two hypotheses will be tested in a hierarchical order at the significance level $\alpha = 0.05$ (two-sided) for the comparison of empagliflozin versus placebo:

$H'_{0,1}$: Mean change in HbA1c (%) from baseline to the end of 26 weeks in regimen starting on empagliflozin 10 mg and either having a dose increase to empagliflozin 25 mg in patients who were non-responders (i.e. patients that did not achieve HbA1c < 7.0%) at Week 12, or who were responders (i.e. patients that did achieve HbA1c < 7.0%) at Week 12 and continue with empagliflozin 10 mg
= Mean change in HbA1c (%) from baseline to the end of 26 weeks in the placebo group.

followed by:

$H'_{0,2}$: Mean change in HbA1c (%) from baseline to the end of 26 weeks in regimen starting on empagliflozin 10 mg and either were responders or were non-responders at Week 12, and continue with empagliflozin 10 mg
= Mean change in HbA1c (%) from baseline to the end of 26 weeks in the placebo group.

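### Should the DINAMO power table have included a standard deviation above 1.0%, given the sponsor's own small paediatric trial?

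*Protocol*

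**What the plan says.** Section 7.7.1 of the protocol names its evidence base: "These estimates are based on available study data in adults with T2DM treated with placebo, linagliptin or empagliflozin". Table 7.7.1: 1 lists five adult trials, two of linagliptin and three of empagliflozin. From these the section concludes that "a mean treatment difference in HbA1c change from baseline of -0.55% with a SD of 0.9% between active drugs and placebo can be assumed".

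Three SDs go into the power table. Of the lower two the protocol says: "For the effectiveness analysis a covariate adjusted standard deviation of 0.9% can be regarded as the expected scenario, while 0.8% will probably be optimistic". The third is introduced thus: "A conservative scenario of 1.0% is added because of the potential of increased variability through the multiple imputations". Table 7.7.1: 2 then gives power for 50 patients per group at two-sided alpha 0.05 (77, 85 and 92% for SD 1.00, 0.90 and 0.80) and at alpha 0.025 (68, 78 and 87%), the latter as a lower bound under Hochberg. The summary presents n = 50 as a balance of clinical, regulatory, ethical, feasibility and statistical considerations, "while maintaining acceptable statistical properties".

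Section 1.2.2 describes the paediatric linagliptin trial 1218.56 in patients aged 10 to 17: 15 treated with placebo, 10 with 1 mg and 14 with 5 mg, HbA1c change at Week 12. There, "the adjusted mean treatment difference between linagliptin 5 mg and placebo was" -0.63 (95% CI -1.50 to 0.23; p = 0.1447). Section 7.7.1 does not refer to this trial.

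Section 7.2.1.2 opens the empagliflozin dose-regimen tests only "After having obtained statistically significant results for both hypotheses" in the primary family. Section 7.7.1 gives no power for that joint event.

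**The concern.** The trial enrols children, yet its planning SDs are entirely adult, and the allowance above 0.9% is explained only by imputation. The protocol contains one source on the variability of HbA1c change in the target age group, for one of the two study drugs at the study dose, and it points to an SD larger than any in the table. If the paediatric SD really is about 1.1%, the row labelled conservative is not conservative at the planned effect, and each comparison has roughly 66 to 70% power instead of 77 to 85%.

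The consequence would extend to the secondary family, since both drugs must succeed before the dose regimens are tested. Someone interpreting a null result, or a secondary family that was never tested, would be judging it against a range of power that omits a plausible paediatric case.

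**Working it through.** **1. The plan's own figures.** Two-sample t-test, n = 50 per arm, df = 98, noncentrality = effect / (SD × √(2/50)). With effect 0.55:

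| SD | alpha 0.05: stated / computed | alpha 0.025: stated / computed |
|---|---|---|
| 1.00 | 77% / 77.7% | 68% / 68.2% |
| 0.90 | 85% / 85.7% | 78% / 78.1% |
| 0.80 | 92% / 92.6% | 87% / 87.5% |

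All six rows reproduce; the stated values are cut to whole percentages.

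**2. The adult SDs.** The arms in Table 7.7.1: 1 total 2,784 patients. The ten raw arm SDs run from 0.76 to 1.03 and pool to 0.88. Nine are below 1.0. These are unadjusted and include values after rescue, whereas the power table uses 1.0 as a covariate-adjusted SD. Against this evidence, 1.0% is on the cautious side.

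**3. The SD implied by trial 1218.56.** Neither the SD, the model nor the analysed numbers are in the documents, so df of 23 to 35 is assumed.

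- SE from the CI = (0.23 + 1.50) / 2 / t(0.975, df) = 0.865 / 2.069 to 0.865 / 2.030 = 0.418 to 0.426.
- SE from the p-value = 0.63 / t for p = 0.1447: 0.417 to 0.422. The two routes agree.
- SD = SE / √(1/n1 + 1/n2). With the treated numbers 15 and 14, the root is 0.3716 and SD = 1.12 to 1.15. With 14 and 13, inferred from the responder percentages (14.3% = 2/14, 30.8% = 4/13), the root is 0.3852 and SD = 1.08 to 1.11.
- The chi-square 95% interval for the SD, across these variants, is about 0.84 to 1.58.

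This is an upper bound on the residual SD, because any baseline imbalance between arms also widens the CI of an adjusted difference. It also depends on the assumed numbers: with 11 or 12 analysed per arm, the same CI gives about 0.97 to 1.04.

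**4. Power at the implied SD, n = 50 per arm.** Power depends on effect divided by SD.

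| Effect | SD | Effect/SD | alpha 0.05 | alpha 0.025 |
|---|---|---|---|---|
| 0.55 (plan) | 1.00 | 0.550 | 77.7% | 68.2% |
| 0.55 | 1.10 | 0.500 | 69.7% | 59.0% |
| 0.55 | 1.15 | 0.478 | 65.8% | 54.7% |
| 0.63 (trial 1218.56) | 1.10 | 0.573 | 80.9% | 72.1% |
| 0.63 | 1.15 | 0.548 | 77.4% | 67.8% |

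The shortfall appears only when the paediatric SD is paired with the adult effect. With effect and SD both taken from the paediatric trial, the standardised effect is 0.548 to 0.573, against 0.550 in the 1.0% row.

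**5. Both primary hypotheses rejected.** Simulation of 2,000,000 trials with a shared placebo arm, common variance, effect 0.55 for both drugs and both p ≤ 0.05 gives 77% at SD 0.9, 66% at 1.0, 56% at 1.10 and 51% at 1.15.

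**The case for a change.** The best argument for amending the section is that a conservative scenario ought at least to reach the point estimate of the only evidence from the target population. Imprecision is a reason to show a sensitivity row, not to leave the trial out. The sponsor holds the report of 1218.56 and could replace the back-solved SD with the exact one. The planned 26-week analysis also includes post-rescue, off-treatment and imputed values, so the protocol's imputation allowance would come on top of any excess variability in children. Even with the larger paediatric effect, power is only about what the 1.0% row shows and stays below the 85% and 78% at the expected SD.

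Much of that stands as fact: section 7.7.1 neither uses the trial nor says why not, and a 1.1% row would have been informative. The joint power is also absent, and it would be so at any SD.

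What does not follow is that the plan misleads. The protocol itself says of the paediatric trial: "Because of the early termination of the study, the trial had limited statistical power". It measured HbA1c at Week 12, not Week 26. Its mean and median differences diverge (-0.63 and -0.80), which leaves room for skew or outliers that would disturb an SD from so few patients. Preferring adult trials with 2,784 patients to a back-solved value from under 30 children is a choice on which competent statisticians differ. Taking that trial's SD while discarding its effect would be selective, since both are imprecise. On joint power, the protocol makes no claim for the secondary family that could be wrong.

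**Conclusion.** No change is needed. The observation is accurate: the planning SDs are adult only, and the paediatric trial suggests an SD near 1.1%. At the planned effect of 0.55% that would lower power per comparison to 70 to 66% (59 to 55% at alpha 0.025). But no stated power is wrong, the interval of about 0.84 to 1.58% contradicts neither 0.9 nor 1.0%, and the paediatric trial's effect and SD together give 81 to 77% (72 to 68%), matching or bettering the 1.0% row.

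Nor would revising the text gain anything. Section 7.7.1 says n = 50 was a compromise in a scarce population, and the log for global amendment 1 ties the move to 50 to an FDA request. Extra rows, a different adjective or a joint-power figure would leave the sample size, the test, the Hochberg procedure and the order of testing untouched, and the precision actually achieved will show in the trial's own confidence intervals.

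This rests on assumed df (23 to 35) and analysed numbers (13/14 or 14/15) for trial 1218.56, normality for the chi-square interval, and a plain t-test with common variance for power. A 1.1% row and the probability of rejecting both primary hypotheses (about 77% at SD 0.9, 66% at 1.0) are useful background for a reader, not corrections.
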